2.8 Handling of Missing Data

All analyses will be based on available data with missing data excluded, unless otherwise stated.

3.0 DESCRIPTIVE ENDPOINTS AND ADDITIONAL DATA

3.1 Baseline and Demographic Characteristics

The baseline and demographic variables will be summarized for the subjects enrolled: gender, age, ethnicity, race, echocardiogram measurements, NYHA class, and 12-lead ECG, etc.

3.2 Adverse Events

All of the adverse device effects, serious adverse device effects, UADEs, USADEs will be summarized for all subjects who enrolled in this trial in terms of the number of events and the percentage of subjects with events. Procedure and device related AEs will also be summarized.

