## Physiologic Pacing Registry Clinical Plan

### 6.3.2 Schedule of Events

**Table 3: Schedule of Events**

CIP Activity	Baseline (≤ 60 days prior to implant)	Implant	1-Month (-14/+30 days post successful implant)	6- Month (±60 days post successful implant)	Unscheduled
Informed Consent Process	X				
Demographics	X				
Physical Examination	X		X	X	X
Cardiovascular History	X				
Implant indication	X				
Medical History	X				
NYHA Class	X		X	X	X
Implant Data Collection (Section 6.2)		X			
System Information		X			
Device Interrogation		X	X	X	X
Device Programming		X	X	X	X
12-lead ECG	X	X*	X	X	X
For His placement only: Measured H wave using device IEGM		X	X	X	X
Measured R wave using device IEGMs through physiologic pacing lead		X	X	X	X
Electro-anatomical Mapping (optional)		(X)			
LVEF (if available)	X			X	
Follow-up Data Collection (Section 6.3)			X	X	
Device Session Records		X	X	X	X
Adverse Event	(X)	(X)	(X)	(X)	(X)
Device Deficiency		(X)	(X)	(X)	(X)
Deviation	(X)	(X)	(X)	(X)	(X)
Termination	(X)	(X)	(X)	(X)	(X)
Assessment for Hospitalization			X	X	X
Death	(X)	(X)	(X)	(X)	(X)
Product Out of Service			(X)	(X)	(X)

(X) if applicable; \*If available

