##### 7.1.2 Serious Adverse Event

If the adverse event meets any of the criteria below, it is regarded as a serious adverse event.

- a) Led to a death,
- b) Led to a serious deterioration in health of the subject, that either resulted in
  1. a life-threatening illness or injury, or
  2. a permanent impairment of a body structure or a body function, or
  3. in-patient hospitalization or prolongation of existing hospitalization, or
  4. medical or surgical intervention to prevent life threatening illness or injury or permanent impairment to a body structure or a body function.
  5. chronic disease
- c) Led to fetal distress, fetal death or a congenital abnormality or birth defect.

**Note:** A planned hospitalization for pre-existing condition, or a procedure required by the CIP, without a serious deterioration in health, is not considered to be a serious adverse event.

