#### 7.2 Procedure and/or Device Relationship

Determination of whether there is a reasonable possibility that the procedure and/or device involved in the registry caused or contributed to an adverse event is to be **determined by the Investigator** and recorded on the appropriate electronic CRF form. Determination should be based on assessment of temporal relationships, evidence of alternative etiology, medical/biologic plausibility, and patient condition (pre-existing condition).

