## Physiologic Pacing Registry Clinical Plan

participation in the registry, or the subject withdraws from the registry. Sites will collect all serious adverse events (including all deaths) and all adverse events related to the procedure and/or device, whether serious or not, throughout the time period defined above and will report to the Sponsor on a CRF. Additional information regarding an adverse event should be updated within the appropriate CRF.

Unchanged, chronic, non-worsening or pre-existing conditions are not adverse events and should not be reported. An off-line form will be made available to allow the investigator to report serious adverse events in the event the entry cannot be made in the EDC. This does not replace the EDC reporting system. All information must still be entered in the EDC system as soon as feasible.

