### Serious Adverse Event Reporting

The investigator will report all serious adverse events, including all deaths, to the Sponsor as soon as possible but no later than outlined below.

Clinical Site	Reporting timelines
All Sites	All serious adverse events must be reported to the Sponsor no later than 3 calendar days from the day the site personnel became aware of the event or as per the investigative site’s local requirements, if the requirement is more stringent than those outlined.

The date the site staff became aware the event met the criteria of a serious adverse event must be recorded in the source document. The Investigator will further report the serious adverse event to the local EC/IRB according to the institution’s EC/IRB reporting requirements.

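### SAP 3.2 names safety summaries only for device- or procedure-attributed events, although sites must report every SAE and death whatever the cause

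*SAP*

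**What the plan says.** **Collection.** Protocol 7.3.1 sets the duty: "Sites will collect all serious adverse events (including all deaths) and all adverse events related to the procedure and/or device, whether serious or not". The subsection on SAE reporting repeats it without a relatedness filter: "The investigator will report all serious adverse events, including all deaths, to the Sponsor as soon as possible", with a limit of 3 calendar days from site awareness. Protocol 7.1.2 lists "in-patient hospitalization or prolongation of existing hospitalization" among the outcomes that make a serious deterioration in health an SAE. Table 3 schedules "Assessment for Hospitalization" at 1 month, 6 months and unscheduled visits.

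**Attribution.** Protocol 7.2 leaves relationship to the site: whether the device or procedure may have played a part is "determined by the Investigator".

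**Planned summaries.** SAP 3.2 has two sentences. The first says that "All of the adverse device effects, serious adverse device effects, UADEs, USADEs will be summarized for all subjects who enrolled in this trial", as event counts and subject percentages. The second says that "Procedure and device related AEs will also be summarized". Outside that section, SAP 3.3 lists deaths among the reasons for early termination, and SAP 2.2 makes a general commitment to describe clinical safety event data.

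**The concern.** Every class named in SAP 3.2 needs a prior judgement that the device or procedure was involved. An SAE that the site investigator considers unrelated is collected and sent to the sponsor within days, but it falls in no named safety summary. Neither document describes independent adjudication of relationship.

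This matters more here than in a study of a well-characterised risk. Protocol 15.4 accepts that physiologic pacing may carry risks not yet known, and attribution is weakest where the risk is not recognised. The background section cites heart failure hospitalization as a harm of conventional RV pacing. An investigator could reasonably call such an admission unrelated to the device, and it would then drop out of the named tables.

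The registry also sets out to compare implants with and without EnSite mapping, across up to 75 centers. A safety contrast built only on attributed events can reflect different attribution habits between sites as well as different event rates. An all-cause SAE count does not need that judgement, and the data for it are already required.

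**Working it through.** No arithmetic in the plan bears on this. SAP 2.4 states that no sample size calculation was made, and no event rate is given anywhere. The check is to compare what is collected with what is named for summary.

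| Event class | Collected? | Named in SAP 3.2? | Elsewhere in the SAP |
|---|---|---|---|
| Related AEs, serious or not | Yes, Protocol 7.3.1 | Yes | Outcome in SAP 1.4 |
| SAEs of any relationship | Yes, Protocol 7.3.1 | No | Only the general wording of SAP 2.2 |
| Deaths from any cause | Yes, Protocol 7.3.1 and 7.3.4 | No | SAP 3.3, as a termination reason |
| Hospitalizations meeting the SAE definition | Yes, as SAEs under Protocol 7.1.2 | No | Only the general wording of SAP 2.2 |
| UADEs, USADEs | No definition or named classifier in either document | Yes | Absent from the abbreviation list |

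Reading across:

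1. SAE appears in the SAP abbreviation list, but the visible body plans no summary of SAEs as such.
2. The death count in SAP 3.3 does not depend on attribution, because Protocol 7.3.4 requires a Withdrawal CRF for every death. No cause, timing or relationship is planned for it, and it is not part of the safety section.
3. Protocol 7.2 asks about relationship only. It does not ask whether an event was anticipated, which is what separates a UADE or USADE from other device effects.
4. SAP 2.5 and 2.6 are redacted and cannot be checked. SAP 3.2, the section headed Adverse Events, is visible.

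**Size.** The number of subjects with an SAE outside the named SAP 3.2 classes is N × p × (1 − a). Here N is the number under surveillance, p the proportion with any SAE by 6 months, and a the proportion of those with an attributed SAE. The documents supply only a ceiling for N: enrollment of up to 1,000 in SAP 1.3, with surveillance starting at attempted implant. They give neither p nor a. Purely as illustration, with assumed values:

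- p = 0.10, a = 0.50: 1,000 × 0.10 × 0.50 = 50
- p = 0.25, a = 0.25: 1,000 × 0.25 × 0.75 = 187.5, about 188

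This range only restates the assumed inputs. It includes fatal cases that SAP 3.3 would count, and the point does not rest on it.

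**The case against.** The strongest reply is that SAP 3.2 does what the protocol asks. The declared safety outcome in Protocol 4.1, repeated in SAP 1.4, is AEs related to procedure or device, and SAP 3.2 summarises those. All-cause SAEs are in no outcome list, and collecting more than is tabulated is not an inconsistency. This stands, so the point is about an incomplete safety summary and not a conflict between the documents.

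Four stronger readings are tempting, and the documents do not support them:

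- *Unattributed SAEs go unused or reach no table.* SAP 2.2 makes a general commitment on safety event data, SAP 3.3 counts deaths, Protocol 15.3 provides for internal safety monitoring of all AEs, and no table shells are shown. What can be said is that no all-cause SAE summary is named.
- *Sites must report every hospitalization and the SAP ignores it.* Table 3 only schedules an assessment. The data list in Protocol 6.3 omits hospitalization, no separate reporting rule is given, and the note in 7.1.2 excludes planned admissions for pre-existing conditions. Only hospitalizations that meet the SAE definition have a clear reporting duty.
- *The UADE and USADE rows cannot be filled, so a zero would mean no assessment.* The sponsor may classify events under procedures not shown, and Protocol 15.0 points to each device's own documentation for known risks. The documents support only that the terms are undefined and no classifier is named.
- *A definite number of subjects is lost from the report.* No rates are given from which to calculate one.

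**Conclusion.** The point holds in limited form. Sites must report all SAEs and deaths irrespective of relationship, while the safety section of the SAP names only summaries that depend on the investigator's attribution. The general sentence in SAP 2.2 does not secure an all-cause table, and the death count in SAP 3.3 is a disposition item.

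The size cannot be stated from the documents. It depends on the SAE rate and on the share attributed, both unknown. The conclusion assumes that the redacted SAP 2.5 and 2.6 contain no all-cause safety summary. The validity of the registry is not in question. The change is worth making because it frees the safety report from sole reliance on attribution, using data already required. The UADE and USADE matter is a secondary point of definition.

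**What to change.** Add to SAP 3.2 a table giving the number of events and the percentage of subjects for:

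- any SAE;
- death from any cause;
- hospitalization meeting the SAE definition in Protocol 7.1.2, as a row of the same table.

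Present each irrespective of relationship and then split by relationship, overall and by EnSite mapping use. State the denominator: SAP 3.2 uses all enrolled subjects, whereas Protocol 7.3.1 starts surveillance at attempted implant.

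As a secondary clarification, define UADE and USADE, state who makes the classification and against what reference, or remove those classes from SAP 3.2.

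The cost is an SAP wording change and a few more tables, with no new site procedure for the all-cause rows. Reported event rates will look higher than with related events alone, so the text should label which rows are all-cause and which are attributed.

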### 5.4 Subject Enrollment

A patient is considered enrolled in the registry once he/she meets eligibility requirements and has signed the informed consent form. Subjects who have a successful implant and are later found to have met exclusion criteria

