### 6.2.1 Unsuccessful Implants and Device Explants

Sites will follow subjects who have an unsuccessful implant of the lead implanted for physiologic pacing for a period of 30 days for procedure-related adverse events and then withdraw the subject from the registry, unless the physiologic pacing lead implant will be re-attempted. Sites should submit all available data for the attempted implant through what was completed during the procedure.

Sites will follow subjects who have their device or lead implanted for physiologic pacing explanted for a period of 30 days for procedure-related adverse events, and then withdraw the subject from the registry.

Sites will withdraw subjects from the registry if a lead implant for physiologic pacing was not attempted – no data collection at implant or following implant is required.

All explanted Abbott devices and Abbott leads should be returned to Abbott to the address below:

Sites must complete and submit a Product Out of Service CRF for any explanted devices to Abbott using the EDC system. After 30 days, if the investigator will not re-attempt implant of a lead for physiologic pacing, sites must complete and submit a Withdrawal CRF and Adverse Event CRF (if applicable) to Abbott using the EDC system.

The physician may re-attempt to implant a lead for physiologic pacing and/or Abbott device at their discretion within 30 days of the initial attempted implant. If the physician chooses to re-attempt the implant, site must complete and submit the associated Implant visit CRFs, an Adverse Event CRF (if applicable) and a Product Out of Service CRF (if applicable) to Abbott using the EDC system.

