#### 7.3 Adverse Event, Device Deficiency, and Complaint Reporting

##### 7.3.1 Adverse Event Reporting

###### General Adverse Event Reporting

Safety surveillance and reporting starts as soon as the patient has an attempted implant in the registry. An attempted implant is defined as insertion of the physiologic pacing lead into vasculature. Safety surveillance and reporting will continue until the last follow-up visit has been performed, the subject is deceased, the subject concludes

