- Incidence of increase in capture threshold of > 1V in leads implanted for physiologic pacing or RV pacing leads
- Far-field atrial oversensing and ventricular oversensing and/or any interventions – including programming – required to address these issues
- NYHA Classification
- LVEF, LVEDV, LVESV (if available)
- Tricuspid and mitral regurgitation severity by echocardiogram (if available)
- Device estimated battery longevity via device session records
- Frequency/burden of detected atrial and ventricular arrhythmias via device session records
- Procedure and device-related adverse events

2.0 **ANALYSIS CONSIDERATIONS**

2.1 **Analysis Populations**

2.1.1 **Enrollment Population**

The enrollment population includes all subjects enrolled (upon providing written informed consent) in the registry.

2.1.2 **Implanted Population**

The implanted population includes subjects enrolled in the registry, implanted with Abbott device, and have an active (programmed on) lead implanted for physiologic pacing post implant.

2.2 **Statistical Methods**

Descriptive analysis will be performed to summarize baseline, procedural, safety and effectiveness endpoints and clinical safety event data. Depending on the type of data (e.g. continuous or categorical), statistical methods described in this section below will be used.

2.2.1 **Descriptive Statistics for Continuous Variables**

For continuous variables (e.g., age, blood pressure, 12-lead ECG, etc.), results will be summarized with the numbers of observations, means, and standard deviations, and in addition, with medians, quartiles, minimums, maximums. The 95% confidence intervals may also be provided for the means, when specified.

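### SAP 3.2 reports device-effect percentages over all consented subjects, although safety surveillance starts only at lead insertion: a small dilution in the favourable direction

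*SAP*

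**What the plan says.** SAP 3.2 takes four categories (adverse device effects, serious adverse device effects, UADEs and USADEs) and has them "summarized for all subjects who enrolled in this trial in terms of the number of events and the percentage of subjects with events". The next sentence, "Procedure and device related AEs will also be summarized", names no population.

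Enrolment comes before any procedure. SAP 2.1.1: "The enrollment population includes all subjects enrolled (upon providing written informed consent) in the registry". Protocol 5.4 adds eligibility: "A patient is considered enrolled in the registry once he/she meets eligibility requirements and has signed the informed consent form". Under Protocol 6.1, consent is taken at a Baseline visit that may fall up to 60 days before implant.

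Surveillance starts later. Protocol 7.3.1: "Safety surveillance and reporting starts as soon as the patient has an attempted implant in the registry", and "An attempted implant is defined as insertion of the physiologic pacing lead into vasculature". Protocol 6.2.1 says of everyone else: "Sites will withdraw subjects from the registry if a lead implant for physiologic pacing was not attempted", adding that "no data collection at implant or following implant is required". Failed attempts are treated differently: the same section follows them for 30 days for procedure-related events.

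The SAP expects never-attempted subjects. Its list of early-termination reasons in SAP 3.3 includes not going ahead with the physiologic lead. The visible text defines only one other population, Implanted (SAP 2.1.2), which requires an Abbott device and an active physiologic lead.

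**The concern.** A device-effect percentage is normally read as a risk among people exposed to the procedure. Here the numerator can come almost only from subjects with a lead insertion, because that is where surveillance begins, while the denominator also counts people who consented and never reached that step. The percentage is then pulled down by a rule written into the plan, and a confidence interval around it would not reveal the shift.

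Neither named population gives a per-attempt rate. Enrollment includes the never-attempted. Implanted leaves out failed attempts, which the protocol does keep under observation. For procedure- and device-related AEs the problem is different: no denominator is stated, so the table could be built in more than one way.

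What is at stake is the accuracy of a descriptive safety table. SAP 2.4 states that the registry tests no hypothesis.

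**Working it through.** The plan states no event rate and no never-attempted share, so there is no figure to reproduce. The check is the dilution identity over a range of assumptions.

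**Inputs**
- N = 1,000 enrolled, the maximum in SAP 1.3.
- f = share of enrolled subjects never attempted. Assumed 2, 5, 10%.
- r = share of attempted subjects with a device effect. Assumed 3, 6, 10%.
- e = share of never-attempted subjects with a reported event. Assumed 0, 1, 2%. It need not be zero, because Protocol Table 3 has a conditional Adverse Event mark in the Baseline column.

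**Formula**
- Reported % = r(1 - f) + e × f.
- Relative understatement = [r - r(1 - f) - e × f] / r = f(1 - e/r). This equals f when e = 0, and the direction is favourable as long as e < r.

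**Results for r = 6%**

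| e | f = 2% | f = 5% | f = 10% |
|---|---|---|---|
| 0 | 5.88% | 5.70% | 5.40% |
| 1% | 5.90% | 5.75% | 5.50% |
| 2% | 5.92% | 5.80% | 5.60% |

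Example at f = 5%, e = 1%: 0.06 × 0.95 + 0.01 × 0.05 = 0.0575. The relative understatement at f = 5% is 5.00, 4.17 and 3.33% for e = 0, 1 and 2%.

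With e = 0 and the same three values of f, r = 3% reads 2.94, 2.85, 2.70% and r = 10% reads 9.80, 9.50, 9.00%.

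**Against sampling error** (exact Clopper-Pearson 95% intervals, the method in SAP 2.2.2; r = 6%, e = 0)

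| f | Events / attempted | 95% CI | Lower half-width (points) | Shortfall r × f (points) |
|---|---|---|---|---|
| 5% | 57/950 | 4.58-7.70% | 6.00 - 4.58 = 1.42 | 0.30 |
| 25% | 45/750 | 4.41-7.95% | 6.00 - 4.41 = 1.59 | 1.50 |
| 30% | 42/700 | 4.36-8.02% | 6.00 - 4.36 = 1.64 | 1.80 |

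Under these assumptions the shortfall reaches the lower half-width only when f is somewhere between 25 and 30%.

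**The case against.** The strongest reply is that most of the added zeros are true. A subject with no lead in the vasculature cannot have an effect of the physiologic lead, so per-enrolled against per-attempt is largely a choice of what to estimate. This stands. A reader might infer that device effects are going unrecorded on any scale, and the documents do not support that. What remains is narrow: a subject who receives an Abbott device without a physiologic lead attempt, or who has an event during venous access or mapping.

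The size is also small. Protocol 5.3.2.1 admits only patients already scheduled for implant, and nothing in the documents points to an f near 25%. A reader might infer a materially misleading safety result; the figures above do not show one.

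The rate is partly recoverable, since event counts are not diluted and SAP 3.3 tabulates termination reasons. But recovery requires every never-attempted subject to be coded under the one matching reason, while death and withdrawn consent are separate entries there.

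SAP 3.2 never uses the word denominator, and SAP 2.8 drops missing data. However, SAP 2.8 yields where something else is stated, and SAP 3.2 names its own set. A subject with no reported event would also ordinarily count as event-free, not as missing. The all-enrolled reading is the natural one.

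SAP 2.5-2.6 and Protocol 8.2.1-8.12 are redacted, so a safety set defined there cannot be excluded, and the claim that none exists would go too far. SAP 2.1 is readable, though, and lists two populations, and SAP 3.2 itself points to enrolled subjects.

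Finally, an attempted-implant denominator has its own bias. Mapping precedes implant, so events in mapping procedures abandoned before lead insertion would leave the rate, and they can occur only in the mapped group of a registry that compares implants with and without EnSite. This objection is sound and shapes the fix.

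**Conclusion.** The point holds as a minor reporting bias. On the visible text, the four device-effect percentages in SAP 3.2 are diluted by a relative f(1 - e/r), or about f if never-attempted subjects report no events. The direction is favourable whenever they report events less often than attempted subjects. With an assumed r of 6% and f of 2 to 10%, the loss is 0.12 to 0.60 percentage points at e = 0 (6.00 - 5.88 and 6.00 - 5.40). None of f, r or e is in the documents, so the actual size is unknown.

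It is mainly dilution rather than missed events, it lies below sampling error for plausible f, and no hypothesis test depends on it. It is still worth correcting, because the shift is systematic and follows from a written rule.

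A reader might extend the finding to procedure- and device-related AEs. The text does not support that: no denominator is given for them, so the fault there is ambiguity, not shown dilution.

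**What to change.** - Add to SAP 2.1 an Attempted-Implant population using the Protocol 7.3.1 definition, regardless of implant outcome.
- Use it as the denominator for the SAP 3.2 device-effect percentages, and state it explicitly for procedure- and device-related AEs.
- Show the enrolled, attempted and implanted counts beside the table, and keep the all-enrolled event counts.
- List events in subjects with no lead insertion separately and by EnSite use, for example when a procedure is abandoned during venous access or mapping. Any with/without-EnSite safety summary should count them, so that the mapped group is not flattered.
- Reconcile the conditional Baseline Adverse Event entry in Protocol Table 3 with the surveillance start in Protocol 7.3.1.

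The cost is SAP wording, one extra listing, one protocol reconciliation and slightly less favourable percentages. One condition needs checking: attempt status must be derivable from the implant and withdrawal CRFs. Protocol 6.2.1 implies that it is, but the visible text does not show the field.
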